2014 Update: Results of this trial were published at the annual Alzheimer's Association International Conference and in the Journal of Alzheimer's Disease in 2012. Results were also used as preliminary data in a NIH K01 Career Development application which was awarded to the PI of this trial in 2014, which builds on these findings. As of December 2014 there are 4 pending grant applications that build on this research. Since the completion of this study, the PI and others have conducted similar research showing the protective effects of RAS acting antihypertensives on multiple outcomes including hippocampal volume, cerebral blood flow, brain inflammatory markers, cognitive function and perhaps most importantly, reduced disease progression from MCI to AD over a 4 year period.

C. 1. Vascular Risk Factors Are Associated with CSF Biomarkers of AD Progression in At-Risk Adults:

In participants at risk for developing AD, higher BMI and total cholesterol levels in men were associated with lower CSF $A\beta_{42}$ levels, suggesting possible gender differences in the effects of vascular risk factors on the pathobiology of AD (Figure 2) [85]. In preliminary baseline data from the ongoing ESPRIT trial (PI: [name]), at risk, ApoE $\epsilon 4$ carriers with increased systolic blood pressure and BMI had CSF $A\beta_{40}$ and $A\beta_{42}$ levels and $A\beta_{40/42}$ ratios suggestive of preclinical disease progression. This relationship was not noted in ApoE $\epsilon 4$ non-carriers (data not shown). Thus, gender and ApoE $\epsilon 4$ may interact with vascular risk factors to influence risk for AD.

C. 2. Successful Recruitment Efforts in Studies Including Lumbar Punctures

Fifty-seven subjects enrolled in the UW IRB approved PAST Pilot and PAST studies, with 50 of those participants undergoing CSF collection. Fifty-one individuals have completed the studies (46 with CSF data). Subjects tolerated the lumbar punctures well without any unexpected adverse effects. Nine of 97 (9.3%) lumbar punctures have resulted in post-lumbar puncture (LP) headaches. We have had no other complications to date. All of these participants willingly chose to continue participating in the study and undergo a follow-up LP, which did not result in headache. Based on our experience, we are confident that the inclusion of lumbar punctures in the proposed study will have no significant effect on recruitment for the proposed trial.

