At baseline and the 4 month follow-up visit, participants will have fasting CSF collected, complete tests of vascular reactivity (**See Vascular Endpoints below**), provide an update on medical problems and medications, review any potential side effects and complete a 1 hour cognitive battery. A fasting blood draw will occur at the baseline visit to assess lipid profile, a potential factor in CSF a-beta levels. While cognitive task performance is not a primary outcome variable, we include this measure because cognition has been linked to BP and antihypertensive medication.

There will be 2 safety visits between the Baseline and Month 4 visits. The safety visits will be at 1) week 1-2 and 2) week 3-4 after the Baseline visit. During the 2 safety visits, participants will have safety labs (creatinine, potassium and urine pregnancy), have blood pressure taken, report any changes in medications or health as well as review and report potential side effects.

The primary endpoint of the proposed study is to determine the effect of ramipril therapy on CSF Aβ levels in a group at risk for developing AD. The secondary endpoints are the effect of centrally acting ramipril therapy on CSF ACE levels, biomarkers of peripheral vascular reactivity as measured by brachial artery flow-mediated vasodilation (FMD) and aortic augmentation index (AAIx) and cognitive task performance. Randomization will be stratified based on sex and APOE genotype, a risk factor for AD. Subjects and investigators will be blinded to the identity of the medication and BP readings obtained throughout the study. [name] will call in ApoE results to the PRC for randomization in order to maintain blinding. Compliance will be assessed by pill count at each of the follow-up visits. The study coordinator will review the possible side effects related to ramipril at each visit, including mild cough, hyperkalemia and changes in kidney function.

All outcomes outlined in the initial protocol, including ApoE testing, have been completed. However, the PI and her collaborators will continue to store all samples and tissue at the UW Madison for future testing.

D. 2. Summary of the Experimental Procedures

D. 2. 1. CSF Collection

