The current study will use state-of-the-art collection techniques that are consistent with the “*NIA Biospecimens Best Practice Guidelines for the Alzheimer’s Disease Centers*” [88]. [name] will perform lumbar punctures on all subjects that do not have contraindications to lumbar punctures (LPs). A neurologist and anesthesiologist will serve as back up for lumbar puncture procedures and LPs will be performed in the fasting state [89]. Subjects will be placed in the sitting position and the skin over L4-L5 will be prepped and draped in a sterile manner. A 25-gauge needle will be used to inject 1% lidocaine as a local anesthetic. A Sprotte 22-gauge spinal needle with introducer will be inserted into the L4-L5 interspace using sterile technique. Between 15-20 ml of CSF will be collected, and divided into four aliquots using four sterile, polypropylene tubes [90] from the UW Laboratory for both collection and storage. CSF samples will be transported to the CTRC processing area immediately after collection and distributed into 0.5 ml aliquots and the fourth CSF sample will be frozen for batched analysis in the Wisconsin Comprehensive Memory Program lab of Drs. [name]. [name], MS, oversees the CSF Bank and has extensive experience in performing LPs. Over the past 5 years, [name] has performed over 250 LPs for research purposes for her own studies as well as the ADNI and ADCS DHA studies. For those participants consenting to storage of future samples, the third tube of CSF will be divided into 0.5 ml aliquots and stored in a -80° C freezer in the Madison VA GRECC for up to 10 years for future testing. Freezers are equipped with backup power and a telephone alarm system.

D. 2. 2. Vascular Endpoints

The primary vascular outcomes are FMD and AAix. [name] (Co-Investigator and Director of the UW Atherosclerotic Imaging Research Program) will oversee collection and analyses of vascular endpoints. Endpoints consist of AAix and brachial artery FMD. FMD is calculated as the ratio of brachial artery diameter after reactive hyperemia to baseline diameter, expressed as percentage change. Intraobserver reliability for measurement of the BA diameter is 0.987, reflecting an interclass correlation coefficient across all readings and conditions [91].

D. 2. 3. Laboratory Evaluation

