Blood, urine and CSF samples will be collected after a 12-hour overnight fast at baseline and month 4 visits. Lipid profile from a fasting blood draw will be done at the baseline visit only. Potassium and creatinine levels will be measured from non-fasting blood draws done at screening and safety visits using enzymatic precipitation techniques on a Hitachi 747 analyzer with standard reagents. These studies will be performed in the UW Hospital Laboratory. Samples will be stored indefinitely and may be used for ongoing Alzheimer’s Disease related research. IRB approval will be obtained for any future use of data or samples not explicitly described in this protocol.

D. 2. 4. Cognitive Testing

Following blood and CSF collection, all subjects will be served a light breakfast. At the Baseline and Month 4 visits, cognitive tests will be administered by a trained technician according to protocols established for each test. The cognitive battery is expected to take 1½ -2 hours to

complete. To reduce practice effects, alternate forms of the above tests have been identified and validated to assure comparability. To control for variations in instrumentation, technicians will be trained to use standardized instructions for each test administered and the same technician will test a particular subject at each visit. In addition, change-scores will be determined for cognitive data obtained at baseline and month 4 visits. The change-scores of the ramipril group will be compared to the change scores of the placebo group. In this way, we will control for practice effects, and maximize internal validity (95). Details of each cognitive test are included in this application.

D. 3. Descriptions of Rationales for Each Specific Aim

D. 3. 1. Specific Aim 1: Effects of Ramipril on CSF A β 40 and A β 42

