D. 3. 4. Rationale for Cognitive Testing A three-year study of 3,217 elderly residents of Cache County, Utah, initially found that the use of some antihypertensive medications at baseline was associated with lower incidence of AD. More recently, ACE-I have been shown to influence cognitive task performance in clinical trials specifically targeting AD related memory problems. Of note, the current proposed study will incorporate the same cognitive outcome measure (the MMSE) that has been shown to be sensitive to ACE-I treatment. Two clinical trials, Syst-Eur and PROGRESS both reported improved cognitive test scores in participants with mild to moderate AD (controlled for vascular dementia) as a result of treatment with ACE-I.

Furthermore, Sink et al. examined the influence of ACE-I that do and do not cross the blood brain barrier (BBB). The authors concluded that BBB crossing ACE-I participants in the BBB crossing group had a significantly lower incidence of developing AD as well as significantly reduced MMSE decline in AD patients compared to CCB and ACE inhibitors. This factor is of particular relevance because the ACE-I in the current proposal, ramipril, is an ACE-I that crosses the BBB. These results were presented at the AGS 2007 Annual Scientific Meeting: Abstract P36. Presented May 5, 2007.

D. 4. Data Analysis and Statistical Considerations The study objective is to evaluate the effects of 4 months of ramipril therapy vs. placebo on mean changes in CSF A β , ACE and mean changes in measures of peripheral endothelial function. While we are not aware of any research examining the effect of ACE-Is on CSF A β , cognitive improvements due to ramipril have been reported in as few as 5 days [29]. In reference to reductions in plasma ACE, ramipril is one of the most potent ACE-Is available and has a trough-to-peak ratio around 50% [106, 107]. When ACE-Is are injected intracerebroventricularly, A β reduction can occur in as few as 2 hours. A sample size of 10 subjects per arm should have greater than 80% power to detect an 8% change in CSF A β , the primary outcome, and greater than 90% power to detect significant

change in endothelial variables. Based on the sample size estimates, 20 subjects will be recruited for the 4-month clinical trial.

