Clinical outcome parameters will be described by means and standard deviations at each measurement time point. Regression models will be used to evaluate predictors of change in CSF variables and endothelial outcomes. Changes in clinical outcome parameters (baseline, month 4) will be analyzed using repeated-measures analysis of variance (ANOVA) to assess the effects of ramipril vs. placebo, using covariates as applicable (ANCOVA). All tests will be two-tailed tests using a significance level of 0.05.

All data for the SEAIRA trial has now been collected at the UW Madison. Data collected as a part of this study will be shared with [name], the prior PI of the SEAIRA study, now Assistant Professor at Emory University. While at Emory University, [name] plans to continue analyses on data collected during her time at the University of Wisconsin. We propose that this study now become a two-site study with [name] mentor and Co-I, [name] as the site PI for the University of Wisconsin. All physical data, data specimens including stored CSF and blood will remain at the UW. The study should however remain open so [name] may continue data analyses for this study. [name] will conduct the analyses at Emory with coded data. The UW ADRC research team will be the only institution with access to this code.

While SEAIRA is now complete, additional analyses on data from this trial need to be conducted. To accomplish this goal, data must be transferred to Emory University from the UW. Data will be sent electronically via email from the ADRC research team at UW Madison to [name] at Emory University. The transfer will be overseen by new UW PI of the project – [name]. All transmitted data will be coded. The code used to label data will be separate from the previously used SEAIRA trial ID number, so that [name] will not know or have access to the key linking identities with the data. Data to be transferred consists of neuropsychological testing data, ApoE4 genotype, abeta and ACE levels and activity in CSF, family history status, race, gender, age, self-reported income category, handedness, education level, drug randomization assignment, symptom reports during the trial, lab data including HDL, LDL, cholesterol levels, potassium, creatine, CSF cell count, smoking history, exercise history, medication and medical history information and data confirming study medication compliance.

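### D.4 does not commit to carrying the stratification factors, sex and APOE, into the ramipril-placebo test; add both as main effects to any remaining change analysis (low severity, cheap)

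*Combined protocol and SAP*

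**What the plan says.** D.1.3 (Study Procedures) states: "Randomization will be stratified based on sex and APOE genotype, a risk factor for AD".

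D.4 (Data Analysis and Statistical Considerations) gives the objective as to "evaluate the effects of 4 months of ramipril therapy vs. placebo on mean changes in CSF" Aβ, ACE and endothelial measures. The arm test is one sentence: outcomes at baseline and month 4 "will be analyzed using repeated-measures analysis of variance (ANOVA) to assess the effects of ramipril vs. placebo, using covariates as applicable (ANCOVA". No covariate is named, and nothing says when one is applicable. A separate sentence adds: "Regression models will be used to evaluate predictors of change in CSF variables and endothelial outcomes"; those predictors are not named either.

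Other places that bear on the point:
- C.1 reports associations of BMI, cholesterol and blood pressure with CSF Aβ levels that differ by gender or APOE ε4 status, "suggesting possible gender differences in the effects of vascular risk factors on the pathobiology of AD". These are cross-sectional.
- D.2.4 has its own rule for cognition: "The change-scores of the ramipril group will be compared to the change scores of the placebo group".
- The 2014 update in section C says that results were published in 2012. D.4 says that "additional analyses on data from this trial need to be conducted", and its list of data to be transferred includes gender, ApoE4 genotype, CSF Aβ and ACE, and treatment assignment. FMD and AAIx are not itemised there.

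**The concern.** With two visits, the arm-by-visit test in a repeated-measures ANOVA is the same as a two-sample comparison of change scores. Baseline is therefore already handled by differencing and is not the issue.

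The issue is the strata. Balancing the arms on sex and APOE makes the arm difference less variable when those factors are prognostic for change. An unadjusted test still counts their variance as noise, so its standard error is too large for the design: it rejects too rarely under the null and can lose power. With 10 subjects per arm there is little precision to give away. Leaving the choice open also lets an analyst who already holds the treatment assignments decide whether the strata go in.

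**Working it through.** **Inputs from the documents.** Two-sided 0.05; 10 per arm; more than 80% power for an 8% change in CSF Aβ (D.4); stratification by sex and APOE (D.1.3); about 70% women expected (E.7.1).

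**Assumptions, because the documents give no figure.** SD of change; correlation r between baseline and month 4 (0.5 to 0.95); stratum effects on change (0, 0.5 and 1 SD per factor); half the subjects APOE ε4 carriers; APOE stratified as carrier or non-carrier; blocks of 2 within four strata.

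**The plan's power figure.** It cannot be reproduced, since no SD is stated. It can be inverted. For a two-sample t test on change with 18 df the noncentrality is d·√(n/2) = d·√5. Power of 0.80 needs d = 1.325, so the SD of change can be at most 8/1.325 = 6.04 percentage points. With SDs of 5, 8 and 10 points, power is 92.2%, 56.2% and 39.5%. The comparisons below start from d = 1.325.

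**Stratum effect on top of that SD.** 20,000 simulated trials per setting, 14 women and 6 men:

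| Effect on change, per factor | Type I error, unadjusted | Power, unadjusted | Power with sex + APOE |
|---|---|---|---|
| 0 | about 0.05 | 0.79-0.80 | about 0.78 |
| 0.5 SD | about 0.04 | about 0.76 | about 0.78 |
| 1 SD | about 0.025 | about 0.64 | about 0.78 |

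If the factors shift the level equally at both visits, the shift cancels in the change: even at 1 SD the unadjusted test keeps power 0.79-0.80 and type I error 0.048-0.051.

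**Stratum effect already inside that SD.** An effect b per factor contributes variance b²(0.7·0.3 + 0.5·0.5) = 0.46b², that is 0.115 at b = 0.5 and 0.46 at b = 1. The residual SD is then √0.885 = 0.941 or √0.54 = 0.735, and the effect in residual units is 1.325/0.941 = 1.41 or 1.325/0.735 = 1.80. Simulated unadjusted power stays at about 0.80-0.83, and adding sex and APOE gains about 2 and 13 points. If b is measured in residual SDs instead, the effect at b = 1 is 1.325·√1.46 = 1.60 and the gain there is about 8 to 9 points.

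**Cost if the strata do nothing.** By the noncentral t with 16 df, power is 79.4% instead of 80%. Simulation, which includes chance imbalance, puts the loss at about 1 to 2 points. By the same formula the adjustment pays for itself once the strata explain about 1.5% of the variance of change.

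**How often the choice changes the verdict.** With a true effect at 80% power and no stratum effect, strata-in and strata-out disagree on p<0.05 in about 4-5% of trials. Reporting the smaller of those two p-values gives type I error 0.057-0.060.

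**Baseline as a further covariate.** A month-4 ANCOVA on baseline, sex and APOE has power of about 0.86, 0.81, 0.79, 0.77 and 0.76 at r = 0.5, 0.7, 0.8, 0.9 and 0.95. With no stratum effect its CI is narrower than the unadjusted change-score CI only below r of about 0.8. The plan's power claim implies r = 1 − 6.04²/(2·CV²), which is 0.82, 0.95 or 0.98 at an assumed between-person CV of 10%, 20% or 30%. In that range baseline adds nothing.

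**The case against.** The strongest reply is that D.4 allows covariates, so sex and APOE are not left out. That stands. A reader might infer that the plan excludes them; the text supports only that it does not commit to them.

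Second, no document shows that sex or APOE affects four-month change. C.1 concerns levels at one time, and a constant shift in level costs nothing. This also stands, so the loss is conditional.

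Third, a reader might attribute to the strata the 9-13% of trials in which an unadjusted change score and a baseline-plus-strata ANCOVA disagree. That would be wrong: baseline alone produces 6-13%, and the strata alone 4-5%. Nor do the figures support requiring the month-4 ANCOVA. At r of 0.9 or more it is 1 to 2 points weaker than strata-adjusted change.

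Fourth, the drop to 0.64 depends on calibration. If the planning SD already contained the stratum variance, power does not fall below plan. That stands, though the unadjusted test remains conservative and the forgone gain remains.

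Fifth, this is a completed, published pilot. D.1.3 says that the protocol outcomes are done, and D.4 does not say that the arm effect will be re-tested. This limits the reach of the fix. It does not remove the point where an arm comparison is still to be made, since the needed CSF and strata data are in the transfer list.

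**Conclusion.** The point holds as a low-severity improvement. Randomization is stratified by sex and APOE, and D.4's arm test does not commit to either factor. If they affect change, the unadjusted test is conservative and gives up power: about 2 points at 0.5 SD per factor and roughly 8 to 14 at 1 SD, depending on how the SD is defined. If they do not, nothing is lost by omitting them.

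The result rests on assumed stratum effects, sex and carrier mix, and block size. A reader might infer that leaving the strata out inflates false positives or undermines the published result. The documents support neither: omission alone errs on the conservative side, and the small excess (0.057-0.060) arises only if the better of the two p-values is chosen after the fact.

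**What to change.** In D.4, for any remaining arm comparison of CSF Aβ and CSF ACE, and of FMD and AAIx where they are analysed:

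1. Include sex and APOE ε4 carrier status as main effects in the change analysis. Leave out their interaction, since four cells average 5 subjects each.
2. Report the arm estimate with its 95% CI.
3. If wanted, list the month-4 ANCOVA with baseline as a sensitivity analysis, noting that it helps only if r is below about 0.8.
4. State which covariates the published analysis used, label the new model post hoc, and report it beside the original. Do not claim that it restores type I error control.

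Cognition stays on change scores as D.2.4 says.

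The cost is a few sentences, 2 degrees of freedom, and about 1 to 2 points of power if the strata do not affect change. For the CSF outcomes no new data are needed.

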C. 3. Preliminary Safety Data in Studies Including Lumbar Punctures in Healthy Adults

Both the PAST Pilot and PAST studies were approved by the UW Human Subjects Committee. All subjects provided informed consent and had intact capacity for medical decision-making (see Appendix for example consent form). As noted above, 9.3% of LPs have resulted in post-LP headaches. We have had no other complications to date. In our studies, we used atraumatic Sprotte 20-gauge spinal needles initially then changed to an even smaller needle, Sprotte 22-gauge. These specific atraumatic spinal needles have been shown in clinical trials to reduce the incidence of post-LP headache. For the proposed trial we will be using either a 22-gauge Sprotte or a 24-gauge Sprotte, depending on the body habitus of the participant. Incidence rates range from 4-6.3% for headaches after procedures using this needle type, depending on the gauge of the needle. Similarly to the current study, the protocols for the 2 studies mentioned above included 4 months of treatment with a medication (cholesterol lowering) vs. placebo in participants at risk for developing AD.

D. Research Design and Methods

This section contains 1) a summary of the experimental protocol and recruitment and 2) a summary of the experimental procedures.

D.1. Summary of Experimental Protocol and Recruitment

D. 1. 1. Participants: Twenty middle-aged, asymptomatic adult children of persons with AD will be randomized for this 4 month RCT. Inclusion/exclusion criteria are listed in **Table 1**. The majority of participants will be recruited from the Wisconsin Comprehensive Memory Program (WCMP) registry. Also, adult children of persons with AD seen in UW Assessment Clinics will be asked by the clinician about participation in this study. These methods have been successfully utilized by all co-investigators in previous clinical trials [85]. Participants may also be recruited via newsletters and information provided at educational seminars.

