Table 2. Dane County, Wisconsin, 2000 Census Data

	Number	%
Race/Ethnicity	Ages 45-64	Ages 45-64
White	85,244	93.7%
Black	2,187	2.4%
Hispanic	1,291	1.4%
Asian/Pacific Islander	1,522	1.7%
American Indian, Eskimo, or Aleut	217	0.2%
Other race	560	0.6%

E. 8. Data Safety and Monitoring

All participants will provide informed consent and the study will be overseen by a Data Safety and Monitoring Board (DSMB) consisting of a physician and statistician who are not directly involved in the study. [name] is a physician who has served on DSMBs and has worked with the PI and Co-Is on previous projects. Similarly, [name] MS, is a biostatistician who has also worked with the PI and Co-Is and has also been directly involved in clinical trials investigating the effects of statins on CSF A β and cognitive outcome variables. Additionally, [name] (Co-I) will serve on the DSMB and will be primary physician involved in this study. All side effects will be closely monitored. The most common side effects of ACE-I are mild cough, hyperkalemia or changes in kidney function. The most common side effect of lumbar puncture (LP) is headache, which is usually self-limited. At UW, the rate of headaches following LP is less than 5%. [name] will perform lumbar punctures for the proposed trial and has significant experience with this procedure, having performed over 260 lumbar punctures in the last five years with no complications. Participants will receive a phone call 24 hours after the LP to inquire about any post-procedure adverse effects. According to the Joint National Committee on Prevention (JNCP) VII guidelines, a dietary intervention for mild BP elevation for 4 months is

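### Does the unsourced post-puncture headache rate in E.8 (below 5%), set against 9.3% elsewhere, call for a change to the plan?

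*Combined protocol and SAP*

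**What the plan says.** Four sections of the combined protocol and SAP give a headache rate after lumbar puncture.

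- C.2, on the two earlier studies: "Nine of 97 (9.3%) lumbar punctures have resulted in post-lumbar puncture (LP) headaches".
- C.3 repeats the percentage and says of the needles behind it that "we used atraumatic Sprotte 20-gauge spinal needles initially then changed to an even smaller needle, Sprotte 22-gauge". It adds a general range: "Incidence rates range from 4-6.3% for headaches after procedures using this needle type, depending on the gauge of the needle".
- E.4.3 presents 9.3% as the rate the team has now and expects it to fall to 5% with a 24-gauge needle.
- E.8 says "At UW, the rate of headaches following LP is less than 5" per cent, without a count, period, needle or citation.

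The needle for this trial is described in three ways. D.2.1 names a 22-gauge needle only. E.4.3 names 24-gauge. C.3 says "we will be using either a 22-gauge Sprotte or a 24-gauge Sprotte, depending on the body habitus of the participant".

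Each participant is due two punctures: "At baseline and the 4 month follow-up visit, participants will have fasting CSF collected" (D.1.3).

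**The concern.** E.8 speaks in the present tense and E.4.3 gives a present rate nearly twice as high. As written, both cannot describe the same experience. The lower figure is the one without a source, and it stands in the section on safety oversight, so someone reading E.8 alone would take away too favourable a picture. The 5% forecast does not rescue it: it depends on a needle that the procedure section does not name, and it is a forecast where E.8 states a fact.

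The number of punctures seems to add to this. C.2 says of the earlier studies "with 50 of those participants undergoing CSF collection", and of those with a headache "All of these participants willingly chose to continue participating in the study and undergo a follow-up LP, which did not result in headache". If the nine headaches belong to nine people, the risk per participant would be 9 of 50, or 18%, far from a figure below 5%. What would be at stake is an understated procedural risk and, if any planning step relied on the low rate, that step too.

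**Working it through.** **1. Reproduce the plan's figure.** From C.2, 9/97 = 0.0928, or 9.3%. This agrees with C.2, C.3 and E.4.3.

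**2. Can 9 of 97 sit with a rate below 5%?**

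- As observed figures, no. 4/97 = 4.1% and 5/97 = 5.2%, so at most 4 headaches would be allowed. Nine headaches need at least 181 punctures (9/181 = 4.97%; 9/180 = 5.0%).
- As evidence on the underlying rate, 5% is not excluded. The Clopper-Pearson 95% limits are the 0.025 quantile of Beta(9, 89), which is 4.3%, and the 0.975 quantile of Beta(10, 88), which is 16.9%. The Wilson interval is 5.0% to 16.7% (lower limit 4.96%).
- If the true rate were 5%, the chance of 9 or more headaches in 97 is 0.054. The data lean towards a higher rate without settling it.

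**3. Could E.8 mean a wider series?** D.2.1 and E.8 mention more than 250 and more than 260 punctures by one operator. Assume, for illustration only, that the nine headaches were the only ones among them: 9/250 = 3.6% and 9/260 = 3.5%. The documents do not say this. It shows only that a wider denominator could yield a figure below 5%.

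**4. The needle sections side by side.**

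| Section | Needle | Rate attached |
|---|---|---|
| C.3, earlier studies | 20-gauge, then 22-gauge | 9.3%, not split by gauge |
| C.3, this trial | 22- or 24-gauge | 4% to 6.3% for the needle type, varying with gauge |
| D.2.1 | 22-gauge | none |
| E.4.3 | 24-gauge | 5%, anticipated |

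The 5% in E.4.3 lies inside the C.3 range, and E.4.3 already ties it to the 24-gauge needle. The gauge itself is inconsistent across three sections. Which is right is not a statistical question.

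**5. The per-participant figure.** 9/50 = 18.0%, if the nine headaches were nine people. C.2 counts punctures and does not say so. Nor do its counts map cleanly to people: 50 had CSF collected and 46 completers had CSF data, and 50 + 46 = 96, not 97.

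A calculation for two independent punctures gives 1 − (1 − 0.0928)² = 17.7%, which looks like support. It is not, because 97 is close to 2 × 50, so 9/50 must come out near 2 × 9/97 = 18.6% whatever the truth. The model also conflicts with the reading it is meant to support. If every affected person had a later puncture without headache, and nobody had more than two punctures (an assumption), all nine headaches fall on first punctures: 9/50 against 0/47. Fisher's exact test gives p = 0.003 against a constant risk per puncture. The 18% should not be quoted as a finding.

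**6. What depends on the E.8 figure?** With 20 participants and two punctures each, there are at most 40 punctures. Expected headaches are 40 × 0.0928 = 3.7 at the observed rate, 40 × 0.05 = 2.0 at the forecast, and 1.6 to 2.5 over the C.3 range. Against the plan:

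- Sample size (D.4): 10 per arm, justified by an 8% change in CSF Aβ, with no attrition term that a headache rate could enter.
- Recruitment (C.2): the judgement that punctures will not hinder it is made beside the 9.3%, not the lower rate.
- Retention: C.2 reports that those with a headache stayed and had their follow-up puncture.
- Monitoring (E.4.3, E.5, E.8): next-day calls and observation after puncture apply to everyone. No headache threshold is set.

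**The case for a change.** The strongest case for a change is that the two present-tense rates contradict each other, one has no support, and the repair is a single sentence. The possible excuses are thin. E.8 identifies no wider series, its operator count comes without a headache count, and an interval that just includes 5% is weak comfort when the tail probability is 0.054. The document is still maintained, so its record could be put right even though data collection has ended. Risk per participant also matters when everyone is punctured twice.

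Most of this stands as a remark on drafting. The E.8 rate lacks a source, and the rate and gauge wording must be reconciled by the sponsor. What does not stand is the weight placed on it. The per-participant figure is an inference from puncture counts, and its apparent confirmation is arithmetic. That such a figure appears nowhere cannot be asserted either, since the consent forms mentioned in E.3 are not part of the text reviewed. E.4.3 already marks 5% as conditional on the needle. Above all, the higher rate is in plain view in C.2, C.3 and the section on puncture risks, so the plan does not hide it.

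**Conclusion.** This is a clerical inconsistency, not a fault in the plan. E.8 gives an unsupported rate below 5% beside a documented 9 of 97 (9.3%, exact 95% interval 4.3% to 16.9%), and three sections differ on needle gauge. The true rate is not shown to exceed 5%, because the interval includes it, the 9.3% pools two gauges, and E.8 may refer to another series. Taking the rates at face value, the difference is about 1.7 expected headaches over 40 punctures (3.7 − 2.0). That assumes all 20 participants have both punctures. Correcting the sentence would alter no estimate, test, sample size or monitoring step, and D.4, E.1 and E.3 state that data collection is finished, so no participant's exposure would change. The sponsor can reconcile the rate and the gauge as a matter of record. No change to the design or analysis follows.
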